SA3. Explore the feasibility of our care delivery model to improve family engagement for cancer risk assessment

- Participants extend invitations to family members to MeTree's family resource center to share results of genetic tests
- Assist with education and referral needed for cascade testing for pathogenic variants

3. Inclusion/Exclusion Criteria

Inclusion

- Receiving medical care at Vanderbilt University Medical Center or Meharry Medical College
- Age 18 years or older
- Able to read and communicate in English
- Willing to use the Internet
- Current My Health at Vanderbilt (MHAV) user or willing to sign up and use (Vanderbilt participant requirement only)

Exclusion

- Non-VUMC/MMC patients
- Diagnosed with a terminal illness
- Unable to speak/read English
- Unable/unwilling to use the Internet (specifically MeTree)
- Previous genetic testing and/or counseling through the Hereditary Cancer Clinic

4. Enrollment

Participants will enroll through My Health at Vanderbilt (MHAV)*. MHAV is VUMC's patient portal where the patient may sign up and participate in managing his/her health care. MHAV can also be used for sending mass research recruitment messages to a predefined cohort of patients who meet certain study-specific inclusion/exclusion criteria, have explicitly said OK to Contact for research purposes, and have an active MHAV account. The messaging process is managed centrally by the VICTR/Health IT teams, sending the messages on behalf of the study team.

MHAV: Initial e-mail notification the patient receives about the research study invitation

1. If patients have email notifications turned on, they will receive the standard, system-generated email stating they have a research invitation.

"You have a new message in My Health at Vanderbilt! Please sign in to read your message.
Thanks for using My Health at Vanderbilt,
Vanderbilt University Medical Center"
2. Once a patient logs in, they will be taken to the research studies dashboard and will see the following patient-friendly study title and description under the heading "Studies you may be able to join".

Once a patient clicks on the link from the email/text notification or from the MHAV homepage, he/she will be taken to the Research Studies page. Here the new study will be listed under the heading – Studies you may be able to join – with the following information (**Appendix H**):

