Once data entry in MeTree is complete all participants will receive a personalized patient report within the platform outlining their familial and genetic risk status the included medical conditions according to current evidence-based guidelines. Participants' providers will be notified via one of several methods (email without PHI, EPIC messaging, or an alert) that their patient has a MeTree clinical decision support report available in the medical chart (accessible via a SMART link). Outside providers will receive an email or letter. The templates for these messages is located in Appendix I. The process to upload the MeTree report and provide accessibility to providers is approved by the Medical Forms Committee and the Center for Health Information Management (CHIM) Committee.

As previously stated, in Aim 2 participants who are identified as at high genetic risk (n=300) will be contacted by the study nurse (as part of their standard of care) to schedule a genetic counseling appointment (Appendix J, High risk patient email). The number and length of genetic counseling appointments will be recorded in order to evaluate the change in clinic capacity for those with a pre-recorded FHH in the MeTree platform as compared to routine patients who have not participated in the study and completed MeTree. The frequency of genetic testing and outcomes of the testing will also be recorded in REDCap from data collection in the Hereditary Cancer Clinic at VUMC.

[figure not shown]
To analyze the time saved by completing MeTree prior to a clinic visit, the study team will perform a retrospective review of control patients, selected by the study team, to assess the amount of time in clinic with the genetic counselors. This will be done through time stamps in eStar and chart review. Control patients will not be a part of the study, nor will their information be shared with anyone. The study team will only review for time spent in clinic versus the study participants' clinic visits.

Additionally, genetic counselors who see participants from this study will be surveyed to better understand their perspective of the use of MeTree. This portion of the study will be in a separate IRB.

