Participants can choose to stop being a part of the study at any time. **Vanderbilt** participants will need to notify the study team either by a phone call to [contact] or email to [contact]. **Meharry** participants will need to **contact** the study manager, [name], at [contact] or [contact].

The participant may be taken out of the study if:

- They do not complete the MeTree Survey within 12 months of enrolling
- If they move out of the state
- Or stop receiving care at VUMC or Meharry Medical College

Withdrawing participation

We will continue to utilize the participant data in analyses unless the participant asks for the data to be withdrawn. Data will still be within the EHR, MeTree, and the research database (REDCap), but data will be excluded from analyses.

Active declining participation

Some participants may begin the study but at some point, feel uncomfortable continuing to participate. Participants who decline to further participate may withdraw from the study if they wish. If the participant declines to continue and alerts the study team, the protocol above will be followed. If the participant declines to proceed any further, study data will continue to be used in pertinent analyses.

Surveys of declination or withdrawal

Participants that decline or withdraw from the study will be asked why they are making this choice.

Non-responders (Passive Decline)

Participants who enroll but do not complete the MeTree questionnaire or subsequent surveys will be treated as enrolled but excluded participants (i.e., non-responders). Participants who are delayed in filling out the questionnaire but still complete the questionnaire prior to analyses of the data will be included, despite the delay.

[figure not shown]
Deceased participants

The study will utilize the data of deceased participants even if they pass before the conclusion of the study.

8. Statistical Considerations

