All data gathered for the proposed studies will be treated with the same degree of confidentiality as a medical record. Confidentiality will be maintained for the identity of participants in this study except as necessary for oversight by the Secretary of the Department of Health and Human Services or his designated representative. Only group information without personal identifiers will be included when sharing process implementation data and outcomes with approved collaborators. FHH data collection is already considered standard of care for medical practice and the risk associated with this information or risk-based prevention strategies is considered to be no more than that associated with routine clinical care.

At the beginning of the study, participants will provide the study team with their VUMC health care provider's name. After the participant completes the MeTree questionnaire, a message will be sent to the provider via REDCap to their eStar message basket alerting them that their patient has completed the questionnaire and that there is a provider-version report available for them to view. The provider can click a link in the message and be sent to MeTree, where they can locate the report.

For contact purposes, we will give participants the option to provide a secondary contact in case the participant cannot be reached. This will only be used if the study team loses contact with the participant (i.e., phone line disconnected, email no longer active).

Regardless of primary or secondary findings, the participant is allowed to provide any findings to their family. The study team will not contact family members of the participants, even in the case of death.

10. Follow-up and Record Retention

The study will last 4 years. Paper records will be kept for up to six years after the study ends. Electronic data will be kept indefinitely. Research data entered into REDCap will be kept for an unknown length of time.

11. Subproject of Family History and Cancer Risk Study (FOREST): Building more inclusive sex- and gender-related questions for genetics research

Table of Contents

1. [Background](#)
2. [Rationale & Specific Aims](#)
3. [Inclusion/Exclusion Criteria](#)
4. [Enrollment](#)
5. [Study Procedures](#)
6. [Reporting of Adverse Events](#)
7. [Study Withdrawal/Discontinuation](#)
8. [Analytic Considerations](#)
9. [Privacy/Confidentiality Issues](#)

1. Background

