### 3. Analytical Population(s)

- a. **Reach population:** defined as the participants who were invited to use MeTree (completed baseline surveys and clicked link to use MeTree)
- b. **Effectiveness population:** defined as the participants who completed MeTree and had a clinical decision support risk report generated.
- c. **Genetic counseling population:** The genetic counseling population includes participants who completed MeTree, received a genetic counseling recommendation and completed the genetic counseling appointment. A random selection of non-study participants with genetic counseling appointments at the same clinic and in the same time frame will be selected, 1:1.
- d. See the protocol paper for additional details of these populations:  
<https://www.sciencedirect.com/science/article/pii/S1551714424002970#f0010>
- e. Study participants had to meet the following inclusion and exclusion criteria to be enrolled in the FOREST study:
  - i. Inclusion
    1. Site: VUMC, MMC
    2. Demographics: Age 18 years or older
    3. Able to read and communicate in English
    4. Willing and able to use the internet to report FHH information
    5. Current user of patient portal (VUMC specific)
  - ii. Exclusion
    1. Not a patient at VUMC or MMC sites
    2. Diagnosed with a terminal illness
    3. Unable to speak/read English
    4. Unwilling or unable to use the Internet to report their FHH information
    5. Report previous genetic testing and/or counseling through the VUMC Hereditary Cancer Clinic
- f. Analyses involving EHR -related information will be restricted to VUMC participants due to the specificity of the EHR-based outcomes.

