## 2. Secondary outcomes derivations and definitions

- a. EHR-based indication for increased cancer risk, defined separate for the time periods

- i. EHR-based variables
  - 1. Variable 1: Personal history code in EHR [Yes/No]
  - 2. Variable 2: Family history code in EHR [Yes/No]
  - 3. Variable 3: Other code in EHR [Yes/No]
- ii. Derived outcomes from the EHR-based variables
  - 1. Variable 4: number of Variables 1-3 with value = Yes
  - 2. Variable 5: at least 1 of Variables 1-3 is Yes
  - 3. Variable 6: number of Variables 1 and 2 with value = Yes
  - 4. Variable 7: at least 1 of Variables 1 and 2 is Yes
- iii. Each of the variables above are defined for two time periods
  - 1. T0 - T1 = before consent through date of consent into the study
  - 2. T1 - T2 = after consent through the end of the study
- iv. Endpoint: Variable 7, at least one of personal history code or family history code, Variables 1 and 2 respectively, are met
- v. Sensitivity Endpoints:
  - 1. Variable 1: Personal history code in EHR
  - 2. Variable 2: Family history code in EHR

- b. Genetic counseling appointment times

- i. Length of genetic counseling appointments

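### The EHR-code endpoint has no level for an unobserved post-consent record, so VUMC participants coded before consent and not seen afterwards would in practice count against MeTree in the McNemar test

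*SAP*

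**What the plan says.** **Who is analysed.** SAP II.3.f limits EHR analyses to one site: they are "restricted to VUMC participants due to the specificity of the EHR-based outcomes". The Effectiveness population (SAP II.3.b) requires a completed MeTree and a generated report, and sets no condition on later EHR contact. Protocol Section 3 requires only "Receiving medical care at Vanderbilt University Medical Center or Meharry Medical College" at entry.

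**Who may stop being observable.** Protocol Section 7 opens its removal list with "The participant may be taken out of the study if" and includes moving out of state and "Or stop receiving care at VUMC or Meharry Medical College". Under the separate heading on withdrawing, it says "We will continue to utilize the participant data in analyses unless the participant asks for the data to be withdrawn". Data from participants who die are also used.

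**How the endpoint is coded.** SAP III.2.a writes its items in the form "Variable 2: Family history code in EHR [Yes/No". Each variable is defined once up to consent and once from consent to study end. Codes from the first window are not carried into the second.

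**Missing data.** SAP III.3 rules out imputation. Its only rule that absence means no concerns relatives' conditions in MeTree, not EHR codes.

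**Test.** SAP IV.3 compares Variable 7 before and after consent by McNemar in the Effectiveness population. SAP IV.5 to IV.7 repeat this in the Reach population and for the two codes separately.

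**The concern.** The site restriction accepts that the outcome can be read only where the record can show it, but it is not carried through to VUMC participants whose record goes silent after consent. A code search of an empty record finds nothing, and a Yes/No variable then reads No. For someone coded before consent, that produces a discordant pair in the direction of MeTree losing an identified person, when all that happened is that the person left VUMC care, moved away or died. At stake is the only between-period test of identification in the SAP: a real gain could be hidden, or an absence of change could appear as a fall. Equal window lengths would not cure this.

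**Working it through.** The plan gives no code rates and no expected counts for this endpoint, so there is no planned figure to reproduce. The 3,000 completers in Protocol Section 8 do follow from 150/(0.10 × 0.50), but that figure does not bear on this point.

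**Notation.** N = VUMC completers; p = share coded before consent; r = share of those recoded if observed; g = share of the uncoded newly coded if observed; f = share with no post-consent VUMC record, assumed to have the same p. All values are assumptions. The SAP states neither alpha nor sidedness; 5% two-sided is assumed, without continuity correction.

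- Gains (No to Yes) = N(1−f)(1−p)g
- Losses (Yes to No) = N(1−f)p(1−r) + Nfp
- Z = (gains − losses)/√(gains + losses)

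**Step 1: who becomes a loss.** Take N = 2,500, p = 20%, f = 10%. Of the 250 unobserved, 250 × 0.20 = 50 become Yes-to-No. The other 200 are No/No and do not enter McNemar.

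**Step 2: effect on the test**, with r = 80%, g = 10%.

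| f | Gains | Losses, empty record = No | Z | Losses, observed only | Z, observed only |
|---|---|---|---|---|---|
| 5% | 190 | 95 + 25 = 120 | 3.98 | 95 | 5.63 |
| 10% | 180 | 90 + 50 = 140 | 2.24 (p = 0.025) | 90 | 5.48 |
| 20% | 160 | 80 + 100 = 180 | −1.08 | 80 | 5.16 |

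At f = 10% the net change is (180 − 140)/2,500 = +1.6 points, against (180 − 90)/2,250 = +4.0 among the observed.

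**Step 3: other inputs.** At f = 10% with p = 10%, Z is 8.03 against 10.01 among the observed; with p = 30% it is −2.74 against 1.32. With N = 2,000, p = 20%, r = 90%, g = 5%, gains and losses are 80/40, 76/58, 72/76 and 64/112 at f = 0, 5, 10 and 20%, with chi-square 13.33, 2.42, 0.11 and 13.09 (the last against MeTree).

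**Step 4: direction.** If d is the net change among the observed, the analysed net change is (1−f)d − fp. Check: 0.9 × 4.0 − 0.1 × 20 = 1.6. Since d cannot be below −p, this never exceeds d. The direction does not depend on the rates. The sign turns at f = d/(d + p): 4/24 = 16.7% in Step 2, and 2/22 = 9.1% in the 2,000-completer case.

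**Step 5: no true change.** Take p = 20%, r = 70% and g = 0.20 × 0.30/0.80 = 7.5%, so observed gains equal observed losses. With N = 2,500 the test rejects about 9%, 30% and 80% of the time at f = 2, 5 and 10%, almost always towards an apparent fall. With N = 1,000 it rejects about 7%, 15% and 42%.

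**Step 6: unobserved in both windows.** With the 2,000-completer inputs, such people are all No/No. Gains and losses are then 76/38, 72/36 and 64/32 at f = 5, 10 and 20%, with chi-square 12.7, 12.0 and 10.7, all favouring MeTree.

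**The case against.** A reader might infer that every VUMC participant with an outside provider is counted as a loss. Protocol Section 5 does foresee such providers ("Outside providers will receive an email or letter"), but a provider who is outside in both windows leaves the VUMC record without that provider's codes in both. The pair is mostly No/No, and Step 6 shows that the reversal then disappears. Nor can it be said that such participants could never move from No to Yes. They receive VUMC care at entry, and Section 5 has the study nurse contact high-risk participants to arrange counseling, with testing data taken from the VUMC clinic. This objection stands in full.

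Three further limits also stand. Scoring an empty record as No is inferred from the Yes/No coding; the SAP states no rule. Retention of leavers is possible, not certain: removal is discretionary, and the sentence on keeping data appears under voluntary withdrawal. SAP II.3.d refers to a separate paper for population details, which was not available here.

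It can also be said that the losses exist only because earlier codes are not carried forward. That is true, but carrying them forward would leave only gains possible, which is a different endpoint. A thin pre-consent record could bias in MeTree's favour, so observability matters in both windows.

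None of this answers the participant coded before consent and unseen afterwards.

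**Conclusion.** The point holds for loss of observation after consent. Nothing in the plan requires a post-consent VUMC record or says how its absence is scored, and the natural reading of the coding biases Secondary Endpoint 1 against MeTree. Only unobserved participants with a pre-consent code become losses; their share of the unobserved equals the pre-consent code rate.

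The size is unknown. Under the assumed inputs, 5% to 10% unobserved is enough to weaken the test materially, and the sign turns at about 9% to 17%. This supposes that the people concerned were observable before consent and wholly unobserved after it, which the documents neither support nor exclude. A reader might infer from these figures that the trial's result will be reversed; they do not show that. The primary endpoint, a descriptive completion percentage, is unaffected. The problem comes from the SAP's code-based definition: Protocol Section 8 takes the post assessment from the MeTree report, regardless of follow-up time.

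**What to change.** - In SAP III.2.a and IV.3, treat a window with no VUMC encounter as not observed rather than No.
- Add a sensitivity analysis of Secondary Endpoint 1 in Effectiveness participants with at least one VUMC encounter in each window.
- Do not let study-triggered Hereditary Cancer Clinic contacts qualify. A high-risk MeTree result itself prompts them, so counting them would preferentially keep high-risk participants.
- Keep the all-VUMC result alongside, stating that empty windows are read as No there.
- Report how many participants lack post-consent contact, by pre-consent code status and provider affiliation.

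Restricting the main analysis to participants who named a VUMC provider would not do. Someone who later leaves VUMC named one at enrolment and stays in the set. Protocol Section 9 says "participants will provide the study team with their VUMC health care" provider's name, so that field may not separate the groups.

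The cost is SAP wording and one encounter query. The sensitivity analysis has a smaller number and selects to some degree on post-consent contact, since people who return may differ in their chance of being coded. That should be stated as a limitation.

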## III. OUTCOMES AND DATA COLLECTION

### 1. Primary outcome derivations and definitions

- a. Completion of MeTree, occurs when a participant provides sufficient information to MeTree to generate a clinical decisions risk support report that is captured and logged in the study database

## 2. Secondary outcomes derivations and definitions

- a. EHR-based indication for increased cancer risk, defined separate for the time periods

- i. EHR-based variables
  - 1. Variable 1: Personal history code in EHR [Yes/No]
  - 2. Variable 2: Family history code in EHR [Yes/No]
  - 3. Variable 3: Other code in EHR [Yes/No]
- ii. Derived outcomes from the EHR-based variables
  - 1. Variable 4: number of Variables 1-3 with value = Yes
  - 2. Variable 5: at least 1 of Variables 1-3 is Yes
  - 3. Variable 6: number of Variables 1 and 2 with value = Yes
  - 4. Variable 7: at least 1 of Variables 1 and 2 is Yes
- iii. Each of the variables above are defined for two time periods
  - 1. T0 - T1 = before consent through date of consent into the study
  - 2. T1 - T2 = after consent through the end of the study
- iv. Endpoint: Variable 7, at least one of personal history code or family history code, Variables 1 and 2 respectively, are met
- v. Sensitivity Endpoints:
  - 1. Variable 1: Personal history code in EHR
  - 2. Variable 2: Family history code in EHR

- b. Genetic counseling appointment times

- i. Length of genetic counseling appointments

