We will use a case-control design for statistically analyses. Cases are defined as the study participants who have completed the MeTree tool (intervention). We will utilize data from the Hereditary Cancer Clinic registry (IRB # 141203) to fine patients identified at risk of a hereditary cancer syndrome in the usual care (control) and intervention conditions. The control condition utilizes historical data from the participants prior to their enrollment date in FOREST to determine the number and proportion of participants who would be identifiable as at risk without the implementation of MeTree. We believe this is the most effective method to analyze the MeTree platform's effect on hereditary cancer testing and outcomes. Power calculations estimate a sample size of up to 3,500 (minimum of 3,000) is needed to produce statistically significant results.

In the graph below, the blue line represents 90% power to detect the primary endpoint with a p-value of 0.05, the green line, 85% power, and the red, 80% power. The x-axis represents how many participants are identified as being at high risk by MeTree.

In prior studies of primary care populations, on average 20% were newly found to be at high risk (had not previously identified). However, in order to accommodate differences in a population that has a proactive hereditary cancer clinic, we used a lower estimate of 10% for the power analyses. Thus at 10% risk identification and 95% power we estimated that we would need at a minimum 1,000 participants for a single site and 2,000 participants total to detect differences in identification at the 2 sites (Meharry and Vanderbilt). In addition, these participants flow into aim 2. Based on power analysis to detect an increase in clinic capacity, we need to have 150 high risk patients who complete MeTree in Aim 1 to see a genetic counselor in the hereditary cancer clinic at Vanderbilt. At a 10% identification rate and a 50% follow up rate (estimate based on literature review and the clinic's attendance rate), a minimum of 3,000 participants will need to complete MeTree in Aim 1. We are therefore enrolling 3,000-3,500 participants for this study.

Data elements considered for this analysis:

Primary Endpoint: Participant designated as high risk for cancer.

Assessment pre: chart review (any indicator prior to MeTree, not time-frame dependent)

Assessment post: MeTree report (measured when the report is generated, independent of amount of follow-up time)

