### 3. Secondary Endpoint 1: EHR-based identification of hereditary risk pre- and post-MeTree

- a. **Hypothesis:**

- i.  $H_0$ : MeTree has no impact on identification of patients at high risk for hereditary cancer
- ii.  $H_A$ : MeTree impacts the identification of patients at high risk for hereditary cancer

- b. **Analysis:** Descriptive statistics (counts and percentages) will be used to describe the EHR-based indication for increased cancer risk (Variable 7: presence of a personal or family history codes) for the two study time periods: pre-study consent period (T0-T1) to the post-study consent period (T1-T2) within the effectiveness population. Contrast the EHR-based determination of high risk for cancer (Variable 7), between the pre-study consent period (T0-T1) to the post-study consent period (T1-T2) using the McNemar test for paired observations, test statistic and p-value will be reported.

**4. Secondary Endpoint 2:** Genetic counseling appointment length for participants who used MeTree and for randomly selected patients from the same clinic who did not use MeTree.

a. **Hypothesis:**

- i.  $H_0$ : Using MeTree prior to genetic counseling has no impact on genetic counseling appointment length
- ii.  $H_A$ : Using MeTree prior to genetic counseling affects genetic counseling appointment lengths

b. **Analysis:** Descriptive statistics (mean, standard deviation, median and IQR or counts and percentages) will be used to summarize appointment lengths by intervention group. Differences in genetic counseling appointment length between intervention groups will be assessed using the Wilcoxon rank sum test, p-value will be reported

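### Secondary Endpoint 1 is presented as pre- versus post-MeTree but splits the EHR record at consent, so codes entered before any MeTree report exists count in MeTree's favour

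*SAP*

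**What the plan says.** SAP IV.3 gives the endpoint the title "EHR-based identification of hereditary risk pre- and post-MeTree", and its alternative hypothesis is that "MeTree impacts the identification of patients at high risk for hereditary cancer". The outcome is Variable 7: at least one personal or family history code in the EHR. SAP III.2.a.iii defines it in two periods, "T0 - T1 = before consent through date of consent into the study" and "T1 - T2 = after consent through the end of the study". The periods are contrasted in the Effectiveness population "using the McNemar test for paired observations, test statistic and p-value will be reported". SAP II.3.f restricts EHR-based analyses to VUMC participants.

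The protocol describes what lies between consent and the report:

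- **Section 4:** the link to MeTree comes at the end of the pre-MeTree survey, and three weeks are allowed for the questionnaire.
- **Section 5:** participants may first take away a worksheet to collect relatives' histories. Vanderbilt participants who have not opened MeTree by 30 days get weekly reminders for up to 4 weeks.
- **Section 7:** one ground for possible removal is "They do not complete the MeTree Survey within 12 months of enrolling". On late completion it says: "Participants who are delayed in filling out the questionnaire but still complete the questionnaire prior to analyses of the data will be included".
- **Sections 5 and 9:** the provider is alerted after the questionnaire is complete.

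Protocol 8 gives two baseline anchors. The primary endpoint has "Assessment pre: chart review (any indicator prior to MeTree, not time-frame dependent", while the control condition uses data from before the participant's enrolment date.

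**The concern.** The title and hypothesis attribute the change in coding to MeTree, but the dividing date is one on which the participant has not yet used it. Between consent and the first report, neither the participant nor the provider has a MeTree risk result. Routine coding in that interval is nevertheless credited to MeTree, and the slower the participant, the more of it there is. Slow uptake would therefore tend to make the tool look better.

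This is the SAP's main inferential test of whether MeTree improves identification, because the primary endpoint (completion) is reported without inference. The three exploratory sensitivity analyses in SAP IV.5 to IV.7 change the population or the code type but keep the same split, so nothing planned would reveal the effect.

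**Working it through.** **Direction.** Take each person with a code in the gap between consent and first report, and write the status as pre/post.

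| Code before consent | Code after report | Consent split | Report split |
|---|---|---|---|
| No | No | No/Yes | Yes/No |
| No | Yes | No/Yes | Yes/Yes |
| Yes | No | Yes/Yes | Yes/No |
| Yes | Yes | Yes/Yes | Yes/Yes |

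People with no code in the gap are classified alike under both splits. Moving from the consent split to the report split, the No/Yes cell can only shrink and the Yes/No cell can only grow. So the consent split can only raise the difference (No/Yes minus Yes/No).

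**Length of the gap, from the protocol's own limits.**

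- Same-day completion: about 0 days.
- Questionnaire allowance: 3 × 7 = 21 days.
- First reminder threshold plus four weekly reminders: 30 + 4 × 7 = 58 days.
- Point at which removal may be considered: 12 months, about 365 days.

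**Share of the post period lying before the report** = gap ÷ length of T1-T2. The study lasts 4 years (Protocol 10), which is the upper bound for T1-T2; 2 years and 1 year are assumed for later enrollees.

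| Gap | 4 years | 2 years | 1 year |
|---|---|---|---|
| 21 days | 1.4% | 2.9% | 5.7% |
| 58 days | 4.0% | 7.9% | 15.9% |
| 365 days | 25.0% | 50.0% | about 100% |

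These are shares for one participant with that gap, not study averages.

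**Illustrative count of codes in the gap** = N × annual rate × gap ÷ 365.25. The documents give none of the inputs except the candidate gaps. Assumed: N = 2,000 VUMC completers; 3%, 5% or 10% coded per year in routine care; every participant having the stated gap.

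- 21 days: 2,000 × 0.03 × 21/365.25 = 3.4; at 5%, 5.7; at 10%, 11.5.
- 58 days: 2,000 × 0.03 × 58/365.25 = 9.5; at 5%, 15.9; at 10%, 31.8.

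So about 3 to 12 codes at 21 days and 10 to 32 at 58 days. Only people without a pre-consent code become No/Yes pairs, so the number of such pairs is lower.

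**Set against all routine coding.** With the same 2,000 people, 5% per year and an assumed 2-year post period, routine coding gives 2,000 × 0.05 × 2 = 200 codes. The gap holds 5.7/200 = 2.9% of these at 21 days and 15.9/200 = 7.9% at 58 days.

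**The case against.** The consent split is not hidden: the analysis text of SAP IV.3 names it, and IV.5 to IV.7 repeat it. It can also be defended. Aim 1 evaluates a care delivery model. After consent the participant completes a survey and may gather relatives' histories, which could itself prompt a code, and a report-date anchor would put such codes in the baseline. That argument stands as a reason to keep the consent-anchored result. It does not justify describing that result as pre- versus post-MeTree.

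A reader might infer that the SAP simply contradicts the protocol. The documents do not support that. Protocol 8 has both a before-MeTree and a before-enrolment anchor, and the SAP is close to the second. The before-MeTree line also belongs to a different contrast, in which the post-assessment is the MeTree report itself rather than a second window of EHR codes.

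A reader might also infer that the gap alone could produce a significant test. Seventeen No/Yes pairs against none would give an exact two-sided p of 2 × 0.5^17 = 1.5 × 10⁻⁵, but this needs an empty Yes/No cell. The variables are defined separately for each period, so a pre-consent code that is not entered again falls in that cell. Seventeen against 10 gives p = 0.25, and 5 against 0 gives 2 × 0.5^5 = 0.06. Nor is there support for assuming an average gap of two months: the protocol allows three weeks and permits same-day completion. Longer gaps are possible, but their frequency is not given.

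**Conclusion.** The point holds as a mismatch between what the endpoint claims and how it is split, with a bias whose direction is certain and whose size is not known. Codes between consent and first report cannot come from the report, and counting them as post-MeTree can only move the discordant balance towards MeTree. The illustrative counts (about 3 to 12 at 21 days, 10 to 32 at 58 days) rest on an assumed 2,000 completers, an assumed 3% to 10% per year and a uniform gap. With rapid completion the effect is close to nil. No p-value can be forecast.

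It would be wrong to infer that moving the date makes the contrast a clean estimate of MeTree's effect. In the 2-year illustration, more than 90% of routine codes fall after the report and would still be credited to MeTree. The uncontrolled pre-post design with unequal windows is a separate issue. This is a should-fix: a secondary endpoint, a one-directional bias, and a cheap remedy.

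**What to change.** 1. In SAP III.2.a.iii and IV.3, for the Effectiveness population, set T1 to the generation date of the first MeTree report. The word first is needed because Protocol 5 allows updated reports.
2. Confirm that this date is held. SAP III.1.a says the report is captured and logged, but does not name a date variable.
3. Report the consent-anchored Effectiveness result as a sensitivity analysis. The Reach analyses must keep the consent anchor, since non-completers have no report date, and this gives them a like-for-like comparator.
4. Label every consent-anchored result as pre- versus post-consent.
5. Reconcile the two baseline anchors in Protocol 8.
6. Report the distribution of time from consent to first report, so that readers can judge the size of the gap.

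The cost is SAP and protocol wording and one date variable. The downsides are a slightly shorter post period, probably a slightly smaller apparent effect, and two anchors to explain.
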